## **7.8 Discontinuation of Study Therapy after CR**

Discontinuation of treatment may be considered for subjects who have attained a confirmed CR that have been treated for at least 24 weeks with pembrolizumab and had at least two treatments with pembrolizumab beyond the date when the initial CR was declared. Subjects who then experience radiographic disease progression may be eligible for up to one year of additional treatment with pembrolizumab via the Second Course Phase at the discretion of the investigator if no cancer treatment was administered since the last dose of pembrolizumab, the subject meets the safety parameters listed in the Inclusion/Exclusion criteria, and the trial is open. Subjects will resume therapy at the same dose and schedule at the time of initial discontinuation.

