Adverse events will be monitored throughout the trial and graded in severity according to the guidelines outlined in the NCI Common Terminology Criteria for Adverse Events (CTCAE) version 4.0. Treatment with pembrolizumab will continue until documented disease progression, unacceptable adverse event(s), intercurrent illness that prevents further administration of treatment, investigator's decision to withdraw the subject, subject withdraws consent, pregnancy of the subject, noncompliance with trial treatment or procedure requirements, completion of 24 months of treatment with pembrolizumab, or administrative reasons. Subjects who attain an investigator-determined confirmed complete response (CR) may consider stopping trial treatment after receiving at least 24 weeks of treatment. Subjects who discontinue after at least 24 months of therapy for reasons other than disease progression or intolerance or who discontinue after attaining a CR may be eligible for up to one year of re-treatment after they have experienced clinical and/or radiographic disease progression. The decision to retreat will be at the discretion of the investigator if no additional systemic immunotherapeutic treatment was administered since the last dose of pembrolizumab, the subject still meets the safety parameters listed in the Inclusion/Exclusion criteria and the trial remains open.

---

CONFIDENTIAL

*This document is confidential. Do not disclose or use unless authorized.*

After the end of treatment, each subject will be followed for 30 days for adverse event monitoring (serious adverse events will be collected for 90 days after the end of treatment). Subjects who discontinue treatment for reasons other than first disease progression will have post-treatment follow-up for disease status until disease progression, initiating a non-study systemic chemotherapeutic treatment, withdrawing consent, becoming lost to follow-up, death, or 36 months post study registration whichever occurs first. Following first disease progression, subjects will be followed by telephone contact for overall survival until death, withdrawal of consent or 36 months post study registration, whichever comes first. The study will be stopped if greater than 30% of patients discontinue pembrolizumab due to an adverse event or for any patient death related to toxicity.

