### 7.7 Criteria for Removal from Protocol Treatment

Subjects may withdraw consent for protocol treatment and/or study itself at any time for any reason or be removed from the protocol treatment and/or study itself at the discretion of the investigator should any untoward effect occur. In addition, a subject may be withdrawn by the treating investigator or the Sponsor if enrollment into the trial is inappropriate, the trial plan is violated, or for administrative and/or other safety reasons. Specific details regarding discontinuation or withdrawal are provided in Section 10.1.4: Other Procedures.

Treatment may continue until one of the following criteria applies:

- The subject withdraws consent to treatment.
- Confirmed radiographic disease progression

*NOTE: A subject may be granted an exception to continue on treatment with confirmed radiographic progression if clinically stable or clinically improved*

- Unacceptable adverse experiences as described in Section 7.1.1
- Intercurrent illness that prevents further administration of treatment
- Investigator's decision to withdraw the subject
- The subject has a confirmed positive serum pregnancy test
- Noncompliance with trial treatment or procedure requirements
- The subject is lost to follow-up
- Completed 24 months of uninterrupted treatment with pembrolizumab or 35 administrations of study medication, whichever is later.

*NOTE: 24 months of study medication is calculated from the date of first dose. Subjects who stop pembrolizumab after 24 months may be eligible for up to one year of additional study treatment if they progress after stopping study treatment provided they meet the requirements detailed in Section 10.1.5.5*

- Treatment was held for 9 weeks for reasons other than complete response
- Administrative reasons

---

CONFIDENTIAL

*This document is confidential. Do not disclose or use unless authorized.*

Participants will be removed from the protocol therapy when any of these criteria apply. Participants removed from protocol therapy for unacceptable adverse event(s) will be followed until resolution or stabilization of the adverse event. Alternative care options will be discussed with the participant.

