### **10.1.2.6 Tumor Imaging and Assessment of Disease**

Clinical response rates will be the primary measure for assessment of tumor response and as a basis for all protocol guidelines related to disease status (e.g. discontinuation of study therapy). Clinical response will be assessed by direct visualization and scoring of disease burden within the upper aerodigestive tract (**Appendix A: Surgical Scoring and Appendix G: CRFs**).

The burden of disease will be assessed at each direct laryngoscopy/tracheoscopy examination performed in clinic and in the operating room, and the extent of papilloma growth will be measured using an instrument previously described [8, 9]. Briefly, evaluations will be made of five major anatomic sites in the larynx (epiglottis, false cords, ventricle, true cords, and subglottis), which are subdivided into 23 subsites. Four major anatomic sites in the tracheobronchial tree (trachea, tracheostomy site, if present, carina and mainstem bronchus) are divided into 6 subsites. The rating incorporates three components. Number of sites (AS) is the actual number of affected sites. For laryngeal disease, this value can range from 0 to 23. Surface area (SA) involvement at each major site is rated on the following scale: 0 (none), 1 (under 1/3 of area is affected), 2 (under 2/3 of area), or 3 (more than 2/3 of area). For the total of five major sites this value can range from 0 to 15. Extent of lumen obstruction (LO) reflects the degree of airway obstruction at each site, on a similar scale of 0-3. For the total of five major sites this

---

*CONFIDENTIAL*

*This document is confidential. Do not disclose or use unless authorized.*

value can range from 0 to 15. The three components (AS, SA and LO) are summed to yield a single overall rating, but the scores are entered separately into the computer to permit analysis of separate components of the score if desired. The potential range of this scoring system is 0 to 53 for laryngeal disease; the range observed in previous studies was 0 to 43 ([www.clinicaltrials.gov](http://www.clinicaltrials.gov); NCT00571701). Scores for tracheobronchial disease are calculated similarly. The maximum possible AS score is 6. The maximum SA and LO scores are each 12. Therefore, the maximum summed score for tracheo-bronchial involvement is 30. Copies of the scoring sheet pages are included in the appendix, as part of the case report forms (**Appendix A: Surgical Scoring and Appendix G: CRFs**).

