**EITHER:**

- Stopped initial treatment with pembrolizumab after attaining an investigator-determined confirmed CR according to RECIST 1.1, and

---

*CONFIDENTIAL*

*This document is confidential. Do not disclose or use unless authorized.*

- Was treated for at least 24 weeks with pembrolizumab before discontinuing therapy
- Received at least two treatments with pembrolizumab beyond the date when the initial CR was declared

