**AND:**

- Experienced an investigator-determined confirmed clinical and/or radiographic disease progression after stopping their initial treatment with pembrolizumab
- Did not receive any anti-cancer treatment since the last dose of pembrolizumab
- Has a performance status of 0 or 1 on the ECOG Performance Scale
- Demonstrates adequate organ function as detailed in Section 5.1.2
- Female subject of childbearing potential should have a negative serum or urine pregnancy test within 28 days. (Please refer to the study calendar for requirements regarding a pregnancy test 72 hours prior to receiving any dose of study medication upon subject enrollment into the study.)
- Female subject of childbearing potential should be willing to use 2 methods of birth control or be surgically sterile, or abstain from heterosexual activity for the course of the study through 120 days after the last dose of study medication (Reference Section 5.7.2). Subjects of child bearing potential are those who have not been surgically sterilized or have been free from menses for > 1 year.
- Male subject should agree to use an adequate method of contraception starting with the first dose of study therapy through 120 days after the last dose of study therapy.
- Does not have a history or current evidence of any condition, therapy, or laboratory abnormality that might interfere with the subject's participation for the full duration of the trial or is not in the best interest of the subject to participate, in the opinion of the treating investigator.

Subjects who restart treatment will be retreated at the same dose and dose interval as when they last received pembrolizumab. Treatment will be administered for up to one additional year.

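### For patients who stop early after a complete response, Sections 2.1, 7.8 and 10.1.5.5 set conflicting retreatment conditions, and those without RECIST-measurable disease cannot meet the early-CR branch of 10.1.5.5.

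*Combined protocol and SAP*

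**What the plan says.** **Early stop.** Section 2.1 provides: "Subjects who attain an investigator-determined confirmed complete response (CR) may consider stopping trial treatment after receiving at least 24 weeks of treatment". Section 7.8 gives the same option, adds at least two doses after the CR was first declared, and does not name RECIST.

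**Retreatment.** Section 2.1 says that patients who stopped after a CR, or after 24 months, "may be eligible for up to one year of re-treatment after they have experienced clinical and/or radiographic disease progression". Section 7.8 is narrower for patients who stopped after a CR: "Subjects who then experience radiographic disease progression may be eligible for up to one year of additional treatment with pembrolizumab". Section 10.1.5.5 holds the detailed criteria, as two alternative branches plus common conditions:
- EITHER branch (early CR): "Stopped initial treatment with pembrolizumab after attaining an investigator-determined confirmed CR according to RECIST 1.1"
- OR branch (24 months): stable disease or better when treatment stopped after 24 months, with no mention of RECIST.
- Common conditions, on progression: "Experienced an investigator-determined confirmed clinical and/or radiographic disease progression after stopping their initial treatment with pembrolizumab"

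Section 1.0 refers to disease progression without saying of which kind.

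**Basis for disease status.** Section 10.1.2.6 states: "Clinical response rates will be the primary measure for assessment of tumor response and as a basis for all protocol guidelines related to disease status". Inclusion criterion 3 in Section 5.1.2 admits patients whose disease is evaluable by endoscopy alone, including larynx-only disease with enough prior surgery.

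**Stopping for progression.** The only progression entry in the Section 7.7 list is "Confirmed radiographic disease progression".

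**The concern.** The sections differ on two things at once: which CR opens the retreatment route, and which progression triggers it. The differences fall on patients followed by endoscopy, which the protocol makes its main measure of disease. Such a patient may stop under 7.8 on an endoscopic CR, having been told in 10.1.4.1 that restarting is an option, and then be excluded by the criteria in 10.1.5.5.

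At stake are access to up to a year of further pembrolizumab, time on treatment, and the make-up of the second-course safety data.

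**Working it through.** No arithmetic applies to the rules themselves. The check sets the sections side by side and then follows particular patients through them.

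**Conditions after an early stop for CR**

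| Section | CR required | Progression required |
|---|---|---|
| 1.0 | CR, type not given | Type not given |
| 2.1 | Confirmed, investigator-determined | Clinical, radiographic or both |
| 7.8 | Confirmed, RECIST not named | Radiographic |
| 9.2, footnote 4 | CR, type not given; refers to 10.1.5.5 | Refers to 10.1.5.5 |
| 10.1.5.5, EITHER branch with common conditions | Confirmed, by RECIST 1.1 | Clinical, radiographic or both |

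The RECIST condition appears only in 10.1.5.5. The limit to radiographic progression appears only in 7.8.

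**Which measure applies to which site.** Section 10.1.2.6.1 applies volumetric CT to tracheal disease and RECIST 1.1 to pulmonary disease. Its RECIST-driven 12-weekly imaging also covers measurable lymphadenopathy and extra-tracheal disease, but excepts the larynx. Section 9.1, footnote 14, confirms that progression on imaging can come from tracheal volumetry.

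**Patients without RECIST-measurable disease** (CR and progression terms only; the other conditions are assumed met)

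| Patient | 2.1 | 7.8 | 10.1.5.5 |
|---|---|---|---|
| Larynx only; early stop on endoscopic CR; endoscopic relapse | Met | Not met | EITHER branch not met |
| Trachea; early stop on endoscopic CR; relapse | Met | Met if volumetric CT shows progression | EITHER branch not met |
| Either site; stopped after 24 months with stable disease or better; confirmed clinical relapse | Met | Does not address a stop at 24 months | OR branch met |

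**Detection.** Section 10.1.5.4 schedules clinical examination every 8 weeks and imaging every 6 months, and drops required CT after one year of follow-up. Section 9.1, footnote 16, continues six-monthly imaging up to 36 months from registration. Under 7.8, qualifying progression may therefore be found later than an endoscopic relapse and, on the 10.1.5.4 schedule, may not be looked for by CT after the first year.

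**Stopping treatment (separate from retreatment).** Section 7.7 names radiographic progression only. Section 7.1.2 continues drug after endoscopic progression only until the next in-office examination confirms it, and 10.1.2.6 cites discontinuation of therapy as an example of a rule based on clinical response. The three do not give one criterion.

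**The case against.** The best defence is that the protocol shows which section governs. Sections 7.7, 9.2 (footnote 4), 10.1.4.1, 10.1.5.3.1 and 10.1.5.4 all refer retreatment to 10.1.5.5, and 7.8 routes it through the Second Course Phase that 10.1.5.5 defines. On progression, 10.1.5.5 agrees with 2.1, so 7.8 is the outlier. That argument carries some weight for the progression wording. It does not help with the CR wording, because the section everyone is sent to is the one with the RECIST qualifier.

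Retreatment is also at the investigator's discretion, and eligibility and response assessments are monitored centrally. Discretion, however, operates among patients who are eligible; it does not settle who they are. On 7.7, the same list includes the investigator's decision to withdraw a patient. That could cover endoscopic progression, but not as a uniform rule.

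Some stronger readings are tempting and are not supported:
- A reader might infer that laryngeal and tracheal patients can never be retreated under 10.1.5.5 or 7.8. The 24-month branch has no RECIST condition, and tracheal disease can progress on volumetric CT and so meet 7.8.
- A reader might infer that one section demands both a RECIST CR and radiographic progression. None does.
- A reader might infer that sites will certainly treat identical patients differently, or that most complete responders are affected. The documents give no figure for either.

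**Conclusion.** The contradiction is real and limited to the early-stop-for-CR route. Without RECIST-measurable disease, a patient who stops early on an endoscopic CR can meet the CR and progression terms of 2.1 but not the early-CR branch of 10.1.5.5. A larynx-only patient with endoscopic relapse also fails 7.8. The mismatch between 7.7 and Sections 7.1.2 and 10.1.2.6 is a separate, smaller inconsistency about stopping treatment.

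The number of patients is not stated. It could be anywhere from none to all of those who stop early on a CR, and that group is a subset of the 22 adults and roughly 2 to 3 pediatric patients planned (24 to 25 in total). For each patient affected, the difference is between no second course and up to one year of one.

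This rests on two assumptions: that a RECIST CR requires disease which the protocol assesses by RECIST, and that the larynx-only relapse has not spread to sites where CT would show progression.

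A reader might infer that the primary result is at risk. It is not: the two-stage rule in Section 14.1 uses best overall response and does not use the retreatment criteria, and Section 14 specifies no second-course analysis. The point should be corrected, but the primary inference does not depend on it.

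**What to change.** Reconcile Sections 1.0, 2.1, 7.7, 7.8, 9.2 (footnote 4) and 10.1.5.5 so that the qualifying CR and the qualifying progression are the same in every stopping and retreatment rule. State explicitly how each applies to patients with no RECIST-measurable disease, separating larynx-only from tracheal involvement. Check 7.1.2 and 10.1.2.6 against the result. Which rule applies is for the sponsor and investigators to decide.

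The cost is a protocol wording amendment with the usual IRB approval. Aligning the text needs no new procedures and no change to the sample size or the primary analysis.

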## **7.9 Subject Replacement Strategy**

Additional subjects may be enrolled to ensure that the required number of evaluable subjects in each cohort is achieved. A subject that discontinues protocol treatment for first progressive disease or a drug-related AE will not be replaced and will be counted in the evaluable population of subjects for the respective cohort.

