The reason for removal from protocol therapy, and the date the participant was removed, must be documented in the case report form (CRF). The research team also updates the relevant Off Treatment/Off Study information in OnCore; the Coordinating Center updates the relevant information for participating sites.

The End of Treatment and Follow-up visit procedures are listed in Section 9 (Protocol Flow Chart) and Section 10.1.5 (Visit Requirements). After the end of treatment, each subject will be followed for 30 days for adverse event monitoring (serious adverse events will be collected for 90 days after the end of treatment). Subjects who discontinue for reasons other than first progressive disease will have post-treatment follow-up for disease status until disease progression, initiating a non-study cancer treatment, withdrawing consent, becoming lost to follow-up, death, or 36 months post-study registration. After documented first disease progression each subject will be followed by telephone for overall survival until death, withdrawal of consent, or 36 months post-study registration, whichever occurs first.

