## **14.0 STATISTICAL ANALYSIS PLAN**

### **14.1 Statistical Analysis Plan Summary**

The primary endpoint of this trial is to evaluate the overall response rate (ORR:CR+PR) via clinical assessment and/or RECIST criteria for adult patients with measurable disease on CT scan. A Simon two-stage design will be used to minimize the number of adult patients exposed to this regimen and the specific sample size and operating characteristics were chosen to be able to rule out a 15% response rate. The rate chosen for the null hypothesis is based on several considerations:

- 1) There is no effective therapy for the patient population in this protocol.
- 2) This protocol represents the first time that this patient population will receive a systemic treatment option.
- 3) The response rate observed using the regimen under study in this protocol in patients with HPV positive head and neck cancer [10] was 20% with corresponding exact 95% CI (5.7% to 43.7%) and although it is anticipated that the patients in this protocol with benign tumors could experience a higher RR since their tumors are chemotherapy and/or RT naïve, this is still unknown.

In the first stage, accrual will continue until 11 evaluable adult patients are entered. If there are  $\leq 1$  adult patients whose disease shows best overall response of CR/PR, accrual to this trial will be closed with the expectation that there is little evidence that the RR would reach 38%. The probability that the trial will close early is 49% if the true RR is 15%. If there are  $\geq 2$  adult patients whose disease shows best overall response of CR/PR, accrual will continue until a total of 21 adult evaluable patients who started protocol treatment are entered. If there are  $\geq 6$  adult patients among 21 evaluable whose disease shows best overall response of CR/PR, further testing of this regimen will be considered. If the true response rate is 38%, the probability of concluding the regimen is effective is 86%, if the true response rate is 15%, the probability of concluding the regimen is effective is 8%. Allowing 1 adult patient to not begin protocol

---

*CONFIDENTIAL*

*This document is confidential. Do not disclose or use unless authorized.*

treatment or be classified as ineligible, a total of 22 adult patients will be entered. In addition, approximately 2-3 pediatric patients will be entered as an exploratory cohort.

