The primary efficacy population includes all eligible adult patients who begin protocol treatment. ORR will be summarized as a proportion with corresponding exact 95% confidence interval (CI) (if the trial closes to accrual after the first stage), or a corresponding 95% two-stage CI if the trial closes to accrual after the second stage. Best overall response for the pediatric patients will also be summarized.

Another endpoint is to assess adverse events. Adverse events will be classified and graded according to the CTCAE v.4.0. Frequencies of adverse events will be summarized overall and within adult and pediatric subgroups. Another endpoint is to assess quality of life (QOL). QOL will be assessed via self-report questionnaires at the timepoints outlined in the Study Flow Chart. Descriptive statistics from the questionnaires will be summarized across timepoints of assessment overall and within adult and pediatric subgroups. Rates of drop-out/non-response to QOL assessments and corresponding reason will also be summarized across timepoints of assessment. Secondary objectives include assessment of biomarkers in blood and tissue. Descriptive statistics from the assays will be summarized across timepoints of sample collection overall and within adult and pediatric subgroups. Rates of refusal and/or reason sample not obtained will be summarized across timepoints of assessment.

Various correlative studies will also be performed. Tissue and blood will be collected at baseline and at post-baseline timepoints as outlined in Section 9 and 10.1.2.7. Markers from tissue and blood will be summarized descriptively and graphically overall and within adult and pediatric subgroups. Within subject changes in markers will also be analyzed. Twenty-two adult patients with baseline and a post-baseline values provides 80% power to detect .65 SD mean difference (Wilcoxon sign rank test two-sided 0.05 alpha level). Baseline as well as changes from baseline to a post-baseline timepoint will also be compared between patients whose disease responded (CR,PR) and those whose disease did not respond using the Wilcoxon rank-sum test. Twenty two adult patients provides 82% power (using a two-sided 0.05 alphas level test) to detect a 1.4 SD difference in means assuming that 38% of the patients have disease which responds.

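### Could section 7.9 let treated adults who leave early be replaced and dropped from the 11- and 21-patient decision counts?

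*Combined protocol and SAP*

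**What the plan says.** Section 7.9 contains two relevant statements. The first is a permission: "Additional subjects may be enrolled to ensure that the required number of evaluable subjects in each cohort is achieved". The second names those who stay in the count: "A subject that discontinues protocol treatment for first progressive disease or a drug-related AE will not be replaced"; such subjects belong to the evaluable population. Other exits listed in 7.7 and 7.10, such as withdrawn consent, noncompliance, loss to follow-up or an investigator's decision, are not mentioned.

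Section 14.1 sets the first stage so that "accrual will continue until 11 evaluable adult patients are entered", closing the trial with one or no responder. The second stage runs to "a total of 21 adult evaluable patients who started protocol treatment are entered", and six or more responders count as success. On the accrual total it says "Allowing 1 adult patient to not begin protocol" treatment or be found ineligible, and then "a total of 22 adult patients will be entered". The analysis set is explicit: "The primary efficacy population includes all eligible adult patients who begin protocol treatment".

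Section 7.7 keeps leavers under observation: "Subjects who discontinue for reasons other than first progressive disease will have post-treatment follow-up for disease status until disease progression". Section 10.1.5.4 schedules those examinations every 8 weeks. Inclusion criterion 3 in section 5.1.2 requires disease that can be evaluated by RECIST 1.1 or endoscopy at entry.

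**The concern.** A list of two exits that are not replaced invites the inference that every other exit may be. Both decision rules rest on the word evaluable, which no section defines, and the two stages word it differently: stage 1 speaks only of evaluable adults, while stage 2 adds that they started treatment. Evaluable might therefore be taken to require something beyond starting, such as having had a response assessment.

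The adults affected would be those who start treatment and stop, without a confirmed response, for a reason other than first progression or a drug-related adverse event, and who then have no further disease assessment. Examples are death, withdrawal of consent, loss to follow-up, or a move to non-study treatment. If they were replaced and not counted, the response rate among those counted would exceed the rate among all treated adults. The trial would then close early less often, and pass more often, than 14.1 states for an ineffective drug. The decision could also use 21 adults while the reported response rate used 22: six responders are 6/21 = 28.6% in one and 6/22 = 27.3% in the other. The trial is open-label and stage 1 is counted mid-trial, so a loose denominator would matter if it were really loose.

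**Working it through.** **1. The plan's own figures.** Inputs from 14.1: n1 = 11, stop if 1 or fewer respond; n = 21, succeed if 6 or more respond; null rate 15%, target rate 38%.

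- Early closure at 15%: P(X1 ≤ 1) = 0.85^11 + 11 × 0.15 × 0.85^10 = 0.1673 + 0.3248 = 0.492 (stated 49%).
- P(success) = Σ over x = 2 to 11 of P(X1 = x) × P(X2 ≥ 6 − x), with X1 ~ Bin(11, p) and X2 ~ Bin(10, p). At p = 0.15 this is 0.0793 (stated 8%); at p = 0.38 it is 0.857 (stated 86%).

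All three agree.

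**2. What 14.1 implies about the count.** It names two conditions: eligible and started. The efficacy population uses both. The spare adult covers failure of either one, and 21 + 1 = 22 leaves no allowance for treated adults who leave. Stage 2's wording, evaluable and started, fits the same pair if evaluable refers to the baseline requirement in inclusion criterion 3. Two separate conditions are therefore consistent with 14.1 and do not signal a third.

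**3. What 7.9 would do if read the other way.** With 22 adults in all and 21 counted, at most one treated adult can be replaced, and only if the spare has not been used. Hold the all-treated rate at 15% and let q be the replaced adult's chance of response. The rate among those counted is (22 × 0.15 − q)/21.

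| q | Rate among counted | False-go | Early closure |
|---|---|---|---|
| 0 (certain non-responder) | 3.300/21 = 0.1571 | 9.5% | 46.5% |
| 0.075 (half the average) | 3.225/21 = 0.1536 | 8.7% | 47.9% |
| 0.15 (unrelated to response) | 3.150/21 = 0.1500 | 7.9% | 49.2% |

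The second and third rows describe the response the adult would have had by staying. If an adult with no confirmed response is counted as a non-responder, the first row applies.

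**4. With an assumed dropout rate.** The documents give none. Suppose each treated adult leaves without a response with probability d, stayers respond at 0.15/(1 − d), the first leaver is replaced, and later ones count as non-responders. An exact recursion over the 21 places gives a false-go probability of 9.0% and early closure of 47.0% at d = 5%, and 9.4% and 45.7% at d = 10%.

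**5. The 14.1 reading.** If 38% is the rate among all treated adults, power stays at 85.7%. If 38% held only among those who stay, counting leavers as non-responders gives power at 0.38(1 − d): 81.4% for d = 5% and 76.3% for d = 10%.

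**The case for a change.** The strongest case for acting has four parts.

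- The population sentence in 14.1 governs the estimate and its interval, whereas the stage rules use a different, undefined word. That is true as drafting. But the same section's arithmetic on the 22nd adult is about the stage count, and it uses the same two conditions.
- Registrants who never receive treatment have their registration cancelled (section 6.0), so replacement in 7.9 might seem to have a purpose only for treated subjects. Yet 14.1 makes its own allowance for non-starters and ineligible adults, which is a sufficient purpose for 7.9.
- Leavers may lose response assessment without leaving the study: section 10.1.1.8 moves a subject to survival follow-up once new therapy starts, and its review covers surgery. This stands, and it makes the affected group somewhat wider than the removals in 7.10. It does not make them replaceable.
- The cap of one replacement rests on 14.1, while sections 1.0 and 2.1 say only approximately 22 and section 7.9 sets no limit. Two or three certain non-responders replaced would give rates of 23 × 0.15/21 = 0.1643 and 24 × 0.15/21 = 0.1714, with false-go probabilities of 11.2% and 13.1%. With unlimited replacement, the rate among those counted is 0.15/(1 − d), and an assumed 5% to 20% leaving without a response gives 9.7% to 18.0%. These figures are correct, but they require exceeding the adult total in 14.1 on the strength of an inference from silence.

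The list in 7.9 also cannot be exhaustive. Read strictly, it would leave out adults who stop after a confirmed complete response under 7.8, whom nobody would replace as not evaluable.

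**Conclusion.** The point does not call for a change. The gap is an unwritten definition that 14.1 supplies by implication: evaluable means eligible, including disease evaluable at baseline, and started on treatment. Section 7.9 says that two groups are not replaced; it nowhere says that others are. On that reading the decision count and the reported response rate share a denominator, and the stated 49%, 8% and 86% apply to the rate among all treated adults.

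The exposure is small even if the other reading were adopted. Within the 22-adult total, the certain-non-responder case moves the false-go probability by 9.5 − 7.9 = 1.6 percentage points and early closure by 49.2 − 46.5 = 2.7 points, with no effect if leaving is unrelated to response. This rests on the 22-adult total being binding and on an all-treated rate of 15%. Larger effects need enrolment beyond that total and a dropout rate that the documents do not give. Passing the final rule leads only to further testing being considered, and the all-treated response rate with its interval would be reported alongside it.
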